CI – Chief Investigator

CRF – Case Report Form

CTIMP - Clinical Trial of an Investigational Medicinal Product

GCP – Good Clinical Practice

GI – Gastrointestinal

IBS – Irritable Bowel Syndrome

IBS-C – Irritable Bowel Syndrome Constipation Subtype

MRN - Medical Record Number

NUTH – Newcastle Upon Tyne Hospitals

PCF – Participant Consent Form

PI – Principle Investigator

PIS – Patient Information Sheet

QA – Quality Assurance

REC – Research Ethics Committee

SAE - Serious Adverse Event

STP – Scientist Training Programme

UEG – United European Gastroenterology

R&D Ref: 10618 IRAS ID: 331715

STUDY SUMMARY

Study Title	A feasibility study to assess rectal sensitivity using elastic balloon distension versus a rapid rectal barostat bag: is there an agreement in London classification diagnoses?	
Short Trial	Assessing rectal sensitivity with elastic balloon versus rectal barostat	
Study Design	Feasibility study, Non-CTIMP, Randomised Multi-site study	
Study Participants	Inclusion criteria: Aged over 18 years Aged under 90 years Male or nonpregnant female Meets 1 or more of the following indications for anorectal physiology investigations: symptoms of constipation or disorder of evacuation, faecal incontinence, functional anorectal pain, faecal urgency and frequency of moving bowels, constant urge to move bowels. Has had a previous lower gastrointestinal tract investigation (colonoscopy, flexible sigmoidoscopy, defecating proctogram, digital rectal examination, CT colon) in the past 2 years Able to understand written and verbal English Exclusion criteria: Creutzfeldt-Jakob disease Pregnancy Previous rectal surgery Previous pelvic radiotherapy Haemorrhoid banding in past 2 weeks Haemorrhoidectomy in past 10 weeks Reporting of change of bowel habits, rectal bleeding, or weight loss with no endoscopic investigations performed since symptoms commenced History of inflammatory bowel disease History of colorectal or anal cancer Lack of capacity to consent Over 90 years old Under 18 years old Currently or has been involved in a clinical trial investigational medicinal product study within 6 months prior to the start of the study. Unable to understand written and/or verbal English	

Planned Sample Size	30	
Planned Study Period	24 months	
	Objectives	Outcome Measures
Primary	To assess the feasibility of a definitive study which will compare two different measurement methods of rectal sensitivity. These measurement methods include the gold standard rectal barostat test and the more widely used elastic balloon distension test.	As this is a feasibility study, there are no primary outcome measures, only secondary outcome measures.
Secondary	 To assess whether they are any differences in rectal sensitivity diagnoses when using the London classification between the two methodologies (Elastic balloon test versus rectal barostat). To assess the repeatability of the rectal barostat test. To investigate whether patients with larger rectums require the elastic balloon to be inflated to a larger volume, before they feel an urge to defecate. To determine whether the Laborie elastic balloon test or Medtronic elastic balloon test aligns better with the rectal barostat test. To assess study participant eligibility, uptake and dropout rate. To assess study acceptability and tolerability. To assess the costs per study of the two 	 The London Classification diagnoses of each patient when rectal sensitivities are assessed using Laborie system elastic balloon distension versus the rectal barostat, and Medtronic system elastic balloon distension versus the rectal barostat. Percentage of rectal capacity at each sensory threshold per test will be measured to assess repeatability Total rectal volume (mL) measured using the rectal barostat will be recorded to assess correlation between capacity and balloon inflation (mL) at sustained urgency. The number of patients who were eligible to participate in the study. The number of patients who chose to participate in the study. The number of patients who dropped out of the study. The length of time required for the rectal barostat protocol and the elastic balloon distension protocol in clinic

Study protocol: Assessing rectal sensitivity with elastic balloon distension versus rectal barostat. Version 1.5 Date: 16/02/2024

R&D Ref: 10618 IRAS ID: 331715

methodologies to help	•	Costings of rectal barostat test
inform a definitive study (clinic time, analysis time		comparison (costs of barostat bags and any additional staff
and consumables).		time required)
	•	Study acceptability and tolerability assessment.

1.0 BACKGROUND

The gastrointestinal tract contains an abundant supply of sensory nerve endings, including mechanoreceptors, chemoreceptors, and thermoreceptors, which allow for conscious perception of distension and contents^[1]. This sensory function is vital in the rectum, the section of the GI tract responsible for the storage of faeces, as it allows for social control of defecation and the ability to delay the process until we are in a socially acceptable environment. Disturbances in sensory function have been associated with a number of functional GI disorders, such as irritable bowel syndrome (IBS), functional constipation, and faecal incontinence, in which patients can suffer with either rectal hyposensitivity or hypersensitivity, depending on the pathophysiology of their condition^[2].

For example, patients with rectal hyposensitivity often suffer with chronic constipation or IBS-C (constipation subtype), and as a result do not experience a normal urge to defecate^[3]. This can result in faeces sitting within the rectum for prolonged periods of time, which requires removal via the use of laxatives, transanal irrigation, or digital evacuation. Research has demonstrated that in individuals with diminished rectal sensitivity, abnormalities can either be due to alterations in afferent nerve pathways affecting the patient's sensation to stimuli, or increased rectal wall compliance^[4]. Conversely, rectal hypersensitivity is associated with faecal urgency and incontinence, and commonly this patient cohort have poorly compliant and low capacity rectums that can contribute to their symptoms^[5]. Some of these patient may feel sudden urges to defecate, but rather than having abnormalities with the rectal wall itself, instead have symptoms as a result of loose stool migrating from the rectum into the highly sensitive anal canal^[6]. Therefore it can be useful to assess rectal sensitivity in these patient cohorts to further categorise the cause of their symptoms, and help to optimise treatment or management.

The most common assessment of rectal sensitivity in a clinical environment is made by gradually inflating an elastic balloon within the rectum, and measuring the volumes at which the patient reports their first sensation, their normal urge to defecate, and sustained urgency^[7]. This is commonly performed in conjunction to anorectal manometry (ARM), which involves insertion of a catheter into the anorectum, and measuring pressure at rest and during specific manoeuvres to assess the function of the anal sphincters^[8]. Most commercially available catheters for this test also contain the required elastic balloon to assess rectal sensitivities, which can be inflated manually or automatically by the equipment, depending on the model and the manufacturer. The advantages of assessing rectal sensitivities using the elastic balloon in conjunction with ARM is that it is fast and cheap, as it does not require a separate catheter being inserted for the additional test. However, the elastic properties of the balloon mean it is unsuitable to assess rectal compliance^[9]. In our

Study protocol: Assessing rectal sensitivity with elastic balloon distension versus rectal barostat.

services, we use two anorectal manometry systems across NUTH and CDDFT services. In NUTH we use a Laborie Solar High Resolution Manometry System with water-perfused catheters, and in CDDFT we use a Medtronic 3D Solid-State High Resolution Manometry System. Both systems are commercially available across the UK, and use a similar elastic balloon for inflation, however, they utilise different published normal ranges of sensory thresholds.

The rectal barostat is another, more comprehensive, device used to assess rectal sensitivity. It contains a polyethylene bag, which is inserted into the patient's rectum and inflated using a pneumatic pump either continuously or in phasic intervals^[10]. Unlike the elastic balloon, the rectal barostat bag has infinite compliance whilst filling, which allows measurement of rectal compliance and total rectal volume, due to its ability to measure opposing pressure of the rectal wall. This protocol is more time-consuming, and for this reason is not routinely used in clinical practice, however it is considered the gold-standard of assessing sensory thresholds, and has the advantage of adding additional information about the biomechanical properties of the rectal wall^[3].

Once sensory thresholds have been measured, a diagnosis of normal, rectal hypersensitivity, rectal hyposensitivity, or borderline hyposensitivity is made according to the London Classification disorders of rectal sensation^[11]. In this study we aim to identify whether patients receive the same diagnosis, according to the London Classification, regardless of whether the elastic balloon distension or rectal barostat is used. To achieve this, patients attending for their standard rectal sensitivity tests using the elastic balloon will be invited to repeat their study using the rectal barostat, and the diagnosis they receive (normal, hypersensitive, hyposensitive, borderline hyposensitive) will be compared. From this data, an indication of the clinical utility of the rectal barostat can be suggested, depending on whether a patient's diagnoses changes. As well as this, participants will be offered a questionnaire following their clinic appointment, which will include questions on their tolerability of each test, in order to gather information on the feasibility of a larger cohort study in the future.

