3.2 Secondary Objectives

- To assess whether they are any differences in rectal sensitivity diagnoses when using the London classification between the two methodologies (elastic balloon distension test and rectal Barostat test).
- To assess the repeatability of the rectal barostat test.
- To investigate whether patients with larger rectums require the elastic balloon to be inflated to a larger volume, before they feel an urge to defecate.
- To determine whether the Laborie elastic balloon test or Medtronic elastic balloon test aligns better with the rectal barostat test.
- To assess study participant eligibility, uptake and drop-out rate.
- To assess study acceptability and tolerability.
- To assess the costs per study of the two methodologies to help inform a definitive study (clinic time, analysis time and consumables).

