3.3 Outcome Measures

As this is a feasibility study, there are no primary outcome measures, only secondary outcome measures. These include:

- The London Classification diagnoses of each patient when rectal sensitivities are assessed using Laborie system elastic balloon distension versus the rectal barostat, and Medtronic system elastic balloon distension versus the rectal barostat.
- Percentage of rectal capacity at each sensory threshold per test will be measured to assess repeatability
- Total rectal volume (mL) measured using the rectal barostat will be recorded to assess correlation between capacity and balloon inflation (mL) at sustained urgency.
- The number of patients who were eligible to participate in the study.
- The number of patients who chose to participate in the study.
- The number of patients who dropped out of the study.
- The length of time required for the rectal barostat protocol and the elastic balloon distension protocol in clinic
- Costings of rectal barostat test comparison (costs of barostat bags and any additional staff time required)
- Study acceptability and tolerability assessment.

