7.5.3 Anorectal Manometry and Rectal Sensitivity Testing

Participants from NUTH will have anorectal manometry and rectal sensitivity tests as per local procedure using a Laborie Solar High Resolution Manometry System with water-perfused catheters. Participants from CDDFT will have anorectal manometry and rectal sensitivity tests as per local procedure using a Medtronic 3D Solid-State

High Resolution Manometry System. These tests are performed as per standard care, however rectal sensitivity testing will be performed twice more as part of non-standard care.

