7.8 Data Analysis

To investigate whether London Classification diagnoses differs when using the rectal barostat compared to elastic balloon distension, a binary indicator will be used to determine the percentage of patients who's diagnoses were in agreement. To examine this closer, a Fisher's exact test will be used to determine whether the difference in number of diagnoses between the elastic balloon distension and rectal barostat reaches a significance level of p=0.05.

To assess repeatability of sensory thresholds at first sensation, normal urge, and sustained urgency of the rectal barostat, an intraclass correlation coefficient will be calculated for each test.

To identify whether there is a correlation between total rectal capacity and the volume of the elastic balloon at the sensory threshold of sustained urgency, a Pearson's correlation will be calculated to test the strength of the relationship between these variables.

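### Repeat runs are planned but not linked to the diagnosis comparison, so balloon-barostat discordance may mix test-retest noise with device difference

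*Protocol*

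**What the plan says.** Section 1.0 (Background) describes giving each patient a London Classification diagnosis by elastic balloon and by barostat, comparing the two, and drawing an inference: "From this data, an indication of the clinical utility of the rectal barostat can be suggested, depending on whether a patient" changes diagnosis between devices.

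Section 7.8 (Data Analysis) specifies the supporting analysis. First, "a binary indicator will be used to determine the percentage of patients who's diagnoses were in agreement". Second, a Fisher's exact test of whether "the difference in number of diagnoses between the elastic balloon distension and rectal barostat reaches a significance level of p=0.05". Both set one device against the other.

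The protocol also plans repeated measurement, in three places:

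- Section 7.5.3, on manometry and balloon testing, states that "rectal sensitivity testing will be performed twice more as part of non-standard care". With the standard-care run this makes three.
- Section 3.2 has the objective "To assess the repeatability of the rectal barostat test", and section 3.3 supplies its outcome: "Percentage of rectal capacity at each sensory threshold per test will be measured to assess repeatability".
- Section 7.8 analyses that objective: for first sensation, normal urge and sustained "urgency of the rectal barostat, an intraclass correlation coefficient will be calculated for each test".

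Section 7.5.4 leaves the barostat test to local procedure and does not state the number of runs.

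**The concern.** The London diagnosis is obtained by cutting patient-reported sensory thresholds into categories. Any measure that is not perfectly repeatable will move some patients across a cut-off when the same test is run again. A patient whose balloon and barostat diagnoses differ may differ because of the device, because of that noise, or both. The percentage of agreement between devices cannot separate these. Barostat repeatability is itself an objective, so the protocol cannot take the noise to be negligible.

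The planned ICC does not supply the missing comparison. It describes a continuous barostat quantity, whereas the rate of re-diagnosis also depends on how many patients lie near a cut-off. It says nothing about the balloon, whose noise contributes to every discordant pair. A chance-corrected agreement index would not separate noise from device difference either.

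At stake is how the discordance figure is read. Section 2.0 says this study will inform a definitive one, and a discordance rate inflated by retest noise is a poor planning input. Section 3.2 also asks which balloon system aligns better with the barostat. If retest noise moves more diagnoses at one site than at the other, that alone may colour the answer.

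**Working it through.** **Figures in the protocol.** Section 6.3 gives 15 + 15 = 30 participants. Section 2.0 gives 70 patients per site in the service evaluation, with 91.4% normal at NUTH (64/70 = 0.914) and 65.7% hypersensitive at CDDFT (46/70 = 0.657). No expected agreement, margin, power or test-retest correlation is given, so there is no planned figure to reproduce beyond these.

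**Step 1: which analyses use which runs.**

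| Data | Analysis stated in 7.8 | Gives a same-method re-diagnosis rate? |
|---|---|---|
| Balloon and barostat diagnoses | Percentage agreement; Fisher's exact test | No, between devices only |
| Barostat thresholds | ICC | No, continuous scale |
| Two further sensitivity runs (7.5.3) | None | No |

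No section says which run supplies the diagnosis.

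**Step 2: how large retest noise could be.** This is an illustration resting on assumptions. Take two runs with no device difference, so that the underlying thresholds are bivariate normal with correlation r. Apply one common cut-off placed so that a share p falls on one side. Then

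P(diagnosis changes) = 2 × [p − P(both runs on that side)].

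The site shares come from section 2.0. The values of r are assumed.

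| Share p | r | P(both on that side) | P(changes) | Expected of 15 |
|---|---|---|---|---|
| CDDFT 0.657 | 0.7 | 0.541 | 23.2% | 3.5 |
| | 0.8 | 0.563 | 18.8% | 2.8 |
| | 0.9 | 0.591 | 13.2% | 2.0 |
| NUTH 0.914 | 0.7 | 0.867 | 9.5% | 1.4 |
| | 0.8 | 0.875 | 7.8% | 1.2 |
| | 0.9 | 0.886 | 5.6% | 0.8 |

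For example, at CDDFT with r = 0.8: 2 × (0.6570 − 0.5629) = 0.188, and 15 × 0.188 = 2.8.

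Over a wider range of r, from 0.5 to 0.95, the expected number changed runs from 4.6 down to 1.4 of 15 at the CDDFT share and from 1.8 down to 0.6 of 15 at the NUTH share.

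**Step 3: precision.** The Clopper-Pearson 95% interval for an observed agreement of 24/30 (80%) is 61% to 92%. For 12/15 it is 52% to 96%. Discordance of this size is compatible with the noise levels in Step 2, so it could not be attributed to the device without a same-test comparison.

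**The case against.** Several points on the other side have force.

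- **Repeat data are planned.** A reader might infer from section 7.8 that the study has no same-test benchmark at all. The documents do not support that: 7.5.3 adds two sensitivity runs, and barostat repeatability has an objective, an outcome and an ICC. What is missing is the link to the diagnosis. This point stands and sets the limits of the concern.
- **The inference is hedged.** A reader might also infer that a changed diagnosis will be counted as proof of barostat utility. Section 1.0 says only that an indication can be suggested, section 3.1 makes feasibility the primary objective, and section 2.0 leaves the diagnosis question and patient outcomes to a definitive study. No progression rule depends on discordance. This stands too, so the sentence in 1.0 is loose rather than decisive.
- **Comparison of counts.** Under the model above, noise swaps patients symmetrically and the expected number in each category is the same for both devices. The comparison of diagnosis counts is then not systematically driven by noise. That is right; the problem lies with the agreement percentage and how it is read. Whether Fisher's test suits paired data is a separate matter.
- **Detail for an SAP.** Tabulating repeats is often left to an SAP, and one may exist. This answers part of the point. The inference in 1.0, however, is written in the protocol and does not follow from the analysis in 7.8, so it would still need rewording.
- **Limits of the remedy.** Repeats on one device within a session may be less variable than two separate tests with endoanal ultrasound between them (section 7.4), so the benchmark may be too low. With 15 per site it will be imprecise. Section 7.5.3 does not name the device for the extra runs, and barostat repeats are not guaranteed. All of this stands and argues for descriptive use only.

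**Conclusion.** The concern holds in a limited form. The protocol ties an indication of barostat utility to a changed diagnosis, analyses diagnosis only between devices, and leaves its planned same-test repeats unconnected to that comparison. Some of the observed discordance may be retest noise, and the analysis as written could not show how much.

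The size is illustrative: about 2.0 to 3.5 of 15 patients at the CDDFT share and 0.8 to 1.4 of 15 at the NUTH share. It rests on assumed correlations of 0.7 to 0.9, no true device difference, and a single cut-off with two categories, whereas section 1.0 lists four diagnoses. It also takes the service-evaluation shares to apply to the patients recruited. The reading of the extra runs as balloon runs rests on their place in 7.5.3.

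The change is worth making because it improves the analysis of data already planned. It does not expose a failure of the feasibility aim.

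**What to change.** **Section 7.8**

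- Derive the London diagnosis for each run already performed.
- Prespecify which run enters the between-device comparison, for example the first run of each device.
- Beside the balloon-barostat discordance, report the same-method re-diagnosis rate with a confidence interval, for the balloon and, where repeats exist, for the barostat.
- Present these descriptively, and note that same-session repeats may understate the noise between separate tests.

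**Sections 7.5.3 and 7.5.4**

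- State which device the two further sensitivity runs refer to and how many barostat runs are made, so that the available repeats are clear.

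**Section 1.0**

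- Reword the inference so that discordance is read against same-method discordance and clinical utility is left to the definitive study.

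**Cost.** If the extra runs are balloon runs, this is analysis and wording only, with no added procedures. The barostat half depends on repeats that the protocol does not fix. The downside is a more modest claim and an imprecise benchmark at this sample size.

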2.0 RATIONALE

A recent service evaluation was conducted to compare the number of diagnoses of disorders of rectal sensitivity (n=70 per site) across NUTH and CDDFT services, in order to identify whether both pieces of equipment produce similar proportions. In NUTH, the majority of patients (91.4%) were diagnosed as normal, whereas in CDDFT, the majority of patients (65.7%) were diagnosed with rectal hypersensitivity. This suggests a possible difference in how each piece of equipment classifies patients, although the limitations such as two different cohorts of patients being studied, and the relatively small sample size should be acknowledged. This service evaluation supported the need for more research into our normal values and how we assess rectal sensitivity, and questioned whether a rectal barostat could be more appropriate.

There is little research directly comparing the assessment of rectal sensitivity using elastic balloon distension and the rectal barostat. A study by Sauter et al. (2014) assessed 26 healthy volunteers using both the elastic balloon inflation and barostat methodologies to assess rectal sensitivities, by recording volume inflated at first sensation, normal urge, and

sustained urgency. They found there was no agreement between the elastic balloon and barostat recorded volumes, however, this is possibly due to the difference in physical properties and shape at identical volumes, which the study failed to take into account^[12]. There are currently no studies comparing the two devices in a symptomatic population, and no indication whether patients receive different diagnoses depending on what device is used to assess rectal sensitivity. Accurate and comprehensive assessment of disorders of rectal sensation to distension in symptomatic patients is vital, as studies have suggested patients with rectal hyposensitivity treated with biofeedback therapy improved their sensory thresholds and symptom severity^[14], and sensory retraining is of greater utility when treating faecal incontinence than strength training alone^[15].

This feasibility study will help investigate key variables required to inform a future definitive study, which will aim to determine whether patients receive a different diagnosis of rectal sensitivity dependent upon the test used. Moreover, a definitive study will address the potential impact of rectal sensitivity testing methodologies on patient outcomes.

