6.3 Number of Participants

In total 30 participants will be recruited for the study. 15 participants will be recruited at NuTH and 15 at CDDFT. Study recruitment will continue until complete study data has been obtained from 15 participants at each site.

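### With about one abnormal Laborie result expected against about ten hypersensitive Medtronic results, a single percentage agreement per balloon measures different things at the two sites and cannot fairly rank the balloons

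*Protocol*

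**What the plan says.** The Rationale (protocol 2.0) describes a service evaluation set up to "compare the number of diagnoses of disorders of rectal sensitivity (n=70 per site"). Its result was: "In NUTH, the majority of patients (91.4%) were diagnosed as normal, whereas in CDDFT, the majority of patients (65.7%) were diagnosed with rectal hypersensitivity". The same section adds the caveat that "the limitations such as two different cohorts of patients being studied, and the relatively small sample size should be acknowledged".

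Section 6.3 fixes the sample: "15 participants will be recruited at NuTH and 15 at CDDFT". Under 7.5.3 NUTH patients are tested only with the Laborie system and CDDFT patients only with the Medtronic system. Under 5.0 patients stay at their own site. Each balloon is therefore compared with the barostat in 15 patients, and no patient has both balloons. Section 7.1 screens routine referrals on eligibility, without regard to sensory status.

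The first outcome in 3.3 is "The London Classification diagnoses of each patient when rectal sensitivities are assessed using Laborie system elastic balloon distension versus the rectal barostat", with the same comparison listed for Medtronic. Section 3.2 also sets the objective of finding out which of the two balloons corresponds more closely to the barostat. For agreement, 7.8 codes each patient as agreeing or not and takes the percentage who agree. It adds a significance test on the numbers of diagnoses, which is not at issue here.

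**The concern.** Percentage agreement is an average over the balloon results that happen to be in the sample. If nearly all balloon results at one site are normal and most at the other are hypersensitive, the two percentages average over different things. One says mainly how often the barostat also reads normal. The other says mainly how often it upholds a finding of hypersensitivity. A higher figure for Laborie could then come from the mix of results and not from closer correspondence with the barostat, yet 3.2 invites a ranking of the two systems.

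A second consequence concerns the definitive study that this one is meant to inform. For Laborie, a reader of one overall percentage could think that agreement on abnormal diagnoses had been assessed when it rested on one or two patients, or none.

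**Working it through.** The sample size of 30 is given without a calculation, so only 15 + 15 = 30 can be checked. The audit percentages reproduce as whole counts: 64/70 = 91.4% and 46/70 = 65.7%. That leaves 6/70 = 8.6% abnormal at NUTH, all abnormal categories together.

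**Inputs.** Abnormal rate at NUTH 6/70 and hypersensitive rate at CDDFT 46/70 (2.0); n = 15 per system (6.3 with 7.5.3).

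**Expected counts.**
- Laborie: 15 × 6/70 = 1.29 abnormal, and 15 × 64/70 = 13.7 normal.
- Medtronic: 15 × 46/70 = 9.9 hypersensitive.

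**Binomial probabilities for Laborie, n = 15, p = 6/70.**
- No abnormal result: (64/70)^15 = 0.261.
- Exactly one: 15 × (6/70) × (64/70)^14 = 0.367.
- At most one: 0.261 + 0.367 = 0.627 after rounding.
- At most two: 0.868, so three or more: 1 − 0.868 = 0.132.
- Five or more: 0.007.

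**Uncertainty in the audit rate.** The exact (Clopper-Pearson) 95% interval for 6/70 is 3.2% to 17.7%.
- Expected abnormal results: 15 × 0.0321 = 0.48 to 15 × 0.1773 = 2.66.
- Probability of at most one: 92% at the lower limit, 23% at the upper.
- Probability of none: 61% at the lower limit, 5% at the upper.

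**What such counts can show.** When all n results agree, the exact 95% lower limit is 0.025^(1/n).
- One abnormal result, confirmed: 2.5%.
- Two, both confirmed: 0.025^(1/2) = 16%.
- Fourteen normal results, all confirmed: 0.025^(1/14) = 77%.

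The normal results therefore carry real information and the abnormal ones almost none.

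**Effect on the comparison of balloons.** Let c_N be the proportion of balloon-normal patients whom the barostat also calls normal, and c_A the proportion of balloon-abnormal patients given the same diagnosis by the barostat. Suppose, for illustration, that both balloons have the same c_N and the same c_A.
- Expected agreement at NUTH: (64/70) c_N + (6/70) c_A.
- The documents do not say how the other 24 of 70 CDDFT patients were classified. If all were normal, expected agreement there is (24/70) c_N + (46/70) c_A.
- Difference: (40/70)(c_N − c_A) = 0.57 (c_N − c_A).
- If none of the 24 were normal, the factor becomes 64/70 = 0.91.

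Two balloons that perform identically in this sense would thus differ in raw agreement by 0.57 to 0.91 of the gap between c_N and c_A, purely through the mix of results. The difference vanishes only if normal and abnormal results are confirmed equally often.

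**The case against.** The study's primary objective is feasibility, agreement is one of several secondary outcomes, and 2.0 leaves the question of whether diagnosis depends on the test to a definitive study. The expected sample also suits the puzzle raised in the Rationale: it lets the barostat check Laborie normals (about 14) and Medtronic hypersensitives (about 10). Both arguments stand. They lower the severity, and the second supports reporting the two groups separately, since that is how such a check would be read.

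The audit rate may not carry over to eligible, consenting patients, as the protocol's own caveat suggests. That is fair. Even so, the upper limit of the interval gives fewer than three expected abnormal Laborie results, shared among hypersensitivity, hyposensitivity and borderline hyposensitivity.

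A statistical analysis plan, not available here, could supply tables and intervals. But 7.8 already fixes a single agreed/not-agreed percentage as the summary, and 3.2 already states the ranking objective. The point is about what those sections say.

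A reader might infer two stronger things:
- **That the Laborie comparison can show nothing about abnormal diagnoses.** The figures do not support this: three or more abnormal results have a 13% chance, and reclassification of normal results can be seen in about 14 patients.
- **That recruitment should be steered by referral indication.** The documents give no abnormal rate by indication. The Background says that "patients with rectal hyposensitivity often suffer with chronic constipation or IBS-C", which runs from hyposensitivity to constipation and not the reverse. An even split between constipation and incontinence or urgency would leave no place for patients with functional anorectal pain alone, who are eligible under 6.1. It would also distort the eligibility and uptake outcomes.

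**Conclusion.** The point holds as a limit on what the agreement result can be taken to mean. It does not show that the sample size or recruitment plan is wrong for a feasibility study. The Laborie percentage would be dominated by normal results and the Medtronic percentage by hypersensitive ones, so setting them side by side cannot fairly answer the alignment objective in 3.2. A usable estimate of agreement on abnormal Laborie results is unlikely, though not impossible.

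This assumes that the audit rates apply roughly to the patients recruited and that patients' results are independent. The illustration of two equally performing balloons further assumes common confirmation rates and brackets the unreported CDDFT categories. It is a cheap improvement of low severity.

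**What to change.** - **7.8:** for each balloon system, replace the single percentage with the full balloon-by-barostat table of the four London diagnoses. Report separately how often balloon-normal patients are reclassified by the barostat and how often balloon-abnormal patients receive the same diagnosis from it, with counts and exact intervals.
- **3.2 and 3.3:** state that for Laborie the study mainly estimates reclassification of normal results, and that the Laborie versus Medtronic comparison is descriptive only. Separate reporting removes the effect of the mix of balloon results, but the systems are still used in different patients at different sites.

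The cost is a few sentences, with no extra patients, tests or data. The downside is that the intervals will be wide, especially for abnormal Laborie results, and the stated conclusion becomes more modest.
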